- a The open label period starts by the transition visit. It is recommended that there is no time gap between the 2 periods, or as short as possible and if possible less than 2 weeks. In case of start of the open label period at the end of the 96 weeks of the double-blind period, the transition visit will generally coincide with the EOT visit of the double-blind period. Recommended windows: The window for obtaining biological samples at any given visit will be  $\pm 7$  days. All other treatment period assessments should be completed within  $\pm 7$  days of the scheduled visit date relative to the transition visit. Post drug elimination follow-up visits should be  $\pm 7$  days of scheduled visit relative to end of treatment.
- b For a regional or national emergency declared by a governmental agency, contingency measures are included in [Section 17.7](#)
- c End-of-treatment and premature discontinuation visit.
- d For patients discontinuing treatment, 2 post drug elimination follow up visits should be scheduled 2 weeks and 4 weeks after study medication discontinuation and initiation of the drug elimination procedure. When applicable patients who prematurely and permanently discontinue study medication will be asked to continue until the planned end of double-blind period (ie, 96 weeks after randomization)
- e Re-consent before starting open-label period and after confirmed MS relapse and when patients turn adults as per local regulations.
- f During the adverse event reporting process, specific questions about pulmonary symptoms and peripheral neuropathy symptoms will be asked. (Patients will be instructed to alert the treating physician of symptoms suggestive of immunodeficiency)
- g Including systolic and diastolic blood pressure, heart rate, body temperature, weight and height; patient standing in bare or stocking feet. Height and weight is to be documented in the growth charts –Blood pressure (BP) and heart rate to be measured in both the supine and the standing positions (measures taken 3 minutes after supine and 3 minutes after standing). A sphygmomanometer with a blood pressure cuff appropriate to the patient's arm girth is used. Of note, during remote visits, only weight will be collected.
- h Tanner stage to be assessed at every 24 weeks and EOT for all patients (until complete sexual maturity).

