#### **MRI**

All brain scans will be reviewed and interpreted by one or more neuroradiologists at an independent, central facility with no access (ie, blinded) to treatment assignment thereby avoiding bias.

An MRI manual explaining the instructions for standard image acquisition requirements, data transfer, archiving and shipping, and outlining the phantom data approval process will be provided to all centers.

MRI should not be conducted within 2 weeks of steroid administration due to potential interference.

In case of at least 5 new/enlarged T2 lesions at the MRI of Week 24, an additional MRI will be performed at Week 36.

Then, in case of:

- At least 9 new/enlarged T2 lesions at Week 36, or,
- At least 5 new/enlarged T2 lesions on each of the 2 consecutive MRI scans of Week 36 and Week 48, or,
- At least 5 new/enlarged T2 lesions on each of the 2 consecutive MRI scans of Week 48 and Week 72.

Patients will have the option to continue in an open label teriflunomide treatment arm.

(Note: new/enlarged refer to previous scan)

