#### **10.1.3.4 Assessments performed on the EOT or premature treatment discontinuation**

Patients who complete the treatment period or who prematurely discontinue should complete EOT procedures including both safety and efficacy assessments. This visit does not need to be performed when the patient switches to the open label period after a confirmed relapse or high MRI activity (as per protocol criteria). Prematurely discontinued patients are encouraged to participate in an early permanent treatment discontinuation (EPTD): they will be followed for safety until they complete 96 weeks from randomization. This includes discontinuation from the open label period, when it occurs within 96 weeks of randomization.

- EDSS.
- SDMT.

- Cognitive Battery Test.
- Brain MRI.
- Adverse event reporting.
- Vital signs.
- Physical examination.
- ECG 12-leads.
- Tanner staging.
- Clinical routine laboratories (including immunoglobulins and TSH).
- Concomitant medication.
- Accountability / compliance.
- Teriflunomide PK sampling.

Post drug elimination process (ie, prescribing Cholestyramine or Activated charcoal and scheduling for two follow up visits) should be initiated.

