1.4 STUDY PLAN

The study design is briefly described in the following graphical presentation:

R: Randomization

Note: An optional additional extension period with teriflunomide is offered to young patients when they complete the study, to provide treatment until they are 18 years old and/or can switch to commercial product, whichever comes first.

Table 1 - Study schedule for the double-blind period

Variable	Visit
Brain MRI	Screening, Weeks 24, 48, 72 and Week 96/end of treatment (EOT) ^a visit, Week 36 if necessary
EDSS	Screening, randomization, Weeks 24, 48, 72, Week 96/EOT ^a visit, and unscheduled relapse visits
SDMT	Randomization, Weeks 24, 48, 72, and Week 96/EOT ^a visit,
Cognitive Battery Test	Randomization and EOT ^a visit
Clinical Laboratory	Screening, randomization, every 4 weeks up to 24 weeks and then every 6 weeks up to the Week 96/EOT ^a
Vital signs	Screening, randomization, Weeks 4, 8, 12, 24, and every 12 weeks up to Week 96/EOT ^a visit
ECG	randomization, Week 96/EOT ^a and after EOT ^a if abnormality
Immunoglobulins and TSH	Randomization, Weeks 24, 48, 72 and Week 96/EOT ^a visit
PK	Weeks 2, 3, 4, 8, 12, 24, 36 and Week 96/EOT ^a visit
Physical examinations	Screening, randomization, Weeks 12, 24, and every 12 weeks up to Week 96/EOT ^a visit
Tanner assessment	Randomization, at Week 24, 48, 72, and at Week 96/EOT ^a for all patients (until complete sexual maturity).

^a Patients who complete the double-blind treatment period or who prematurely discontinue, should complete EOT visit.

Table 2 - Study schedule for the open-label period

Variable	Visit
Brain MRI	Weeks 48, 96, 144 and Week 192/end of treatment (EOT) ⁰ visit
EDSS	Weeks 24, 48, 72, 96, 120, 144, 168, Week 192/EOT ⁰ visit, and unscheduled relapse visits
SDMT	Weeks 24, 48, 72, 96, 120, 144, 168, Week 192/EOT ⁰ visit
Cognitive Battery Test	Week 96 and Week 192/EOT ⁰ visit
Clinical Laboratory	Transition, Weeks 4, 12, and then every 12 weeks up to the Week 192/EOT ⁰
Vital signs ^b	Transition, Weeks 4, 8, 12, and then every 12 weeks up to the Week 192/EOT ⁰
ECG	Week 192/EOT ⁰ and after EOT ⁰ if abnormality on EOT or ECG could not be performed at EOT (in exceptional circumstances).
Immunoglobulins and TSH	Week 96 and Week 192/EOT ⁰ visit
PK	Weeks 2, 3, 4, 8, 12, 24, 36 and Week 192/EOT ⁰ visit
Physical examinations	Weeks 12, 24, and then every 24 weeks up to the Week 192/EOT ⁰

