2.4.4.2.3 Magnetic resonance imaging (MRI) variables

General rules for MRI variables

The protocol requires that the MRI should not be performed until after a minimum of 14 days following completion of corticosteroid therapy. Thus, MRI values obtained within 14 days of systemic corticosteroid therapy will be excluded from the analysis.

Baseline for MRI variables is defined as the last non-missing, valid MRI value that was measured before or on the day of first administration of IMP in the double-blind period. A previous MRI performed in the 6 weeks preceding randomization could be used as the baseline if performed according to the specifications for this study. For valid MRI values in subsequent post baseline visits, time windows (see [Table 4](#) and [Table 5](#) in [Section 2.5.3](#)) between visits will be used to capture MRI measurements. For multiple records within a visit window, the one closest to the targeted visit date will be used.

Number of lesions

The number of new or enlarged T2 lesions per MRI scan will be analyzed using a negative binomial regression model with robust variance estimation. The model will include the total number of new or enlarged T2 lesions as the response variable, with treatment group, region, pubertal status and age as covariates. In order to account for different numbers of MRI scans performed among patients, the log-transformed number of scans will be included in the model as an offset variable. The robust error variances can be estimated by specifying the patient identifier in the repeated statement using SAS PROC GENMOD. The estimated number of lesions per scan and associated 2-sided 95% confidence interval (CI) will be provided for each treatment group.

The number of T1 Gd-enhancing lesions per MRI scan and the number of new T1 hypointense lesions per MRI scan will be analyzed using a similar negative binomial regression model as described above for T2 lesions.

Volume of lesions and brain

Descriptive statistics of the change from baseline in volume of T2 lesions, T1 hypointense lesions and the percentage change of brain volume in the original scale will be summarized at each visit by treatment group.

The proportion of patients free of new or enlarged T2 lesions

The proportion of patients free of new or enlarged T2 lesions at Weeks 48, 96, 144 and 192 will be summarized based on all patients having an MRI at these time points. Kaplan-Meier methods will be used for estimation.

Censoring rule

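### Patients who switch early after a relapse have no scan scheduled at the switch, and the lesion model's scan-count offset treats their longer intervals as equal to shorter ones

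*SAP*

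**What the plan says.** **Model.** SAP 2.4.4.2.3 fits a negative binomial regression to each patient's total of new or enlarged T2 lesions, and "the log-transformed number of scans will be included in the model as an offset variable". Gd-enhancing and new T1 hypointense lesions get a similar model. The section names no reference scan for a new lesion.

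**Reference scan.** The only statement is a remark attached to the high-MRI-activity switch rule (Protocol 8.1, MRI): "Note: new/enlarged refer to previous scan".

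**Scan schedule.** SAP 1.4 Table 1 puts double-blind scans at screening, Weeks 24, 48, 72 and 96/EOT, with Week 36 if triggered. Table 2 puts open-label scans at "Weeks 48, 96, 144 and Week 192/end of treatment". Neither the transition visit (Protocol 1.3) nor the relapse visit (Protocol 1.2 and 10.1.3.5) lists an MRI.

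**The switch.** Protocol 10.1.3.4 includes a brain MRI at EOT, but says: "This visit does not need to be performed when the patient switches to the open label period after a confirmed relapse or high MRI activity". For patients who finish 96 weeks, "the transition visit will generally coincide with the EOT visit of the double-blind period" (Protocol 1.4), so they have a scan at the switch.

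**Span of the count.** SAP 2.1.3.2 lists the MRI endpoints among those belonging to the open-label period. SAP 2.4.4 assesses effects from randomization unless otherwise noted, and 2.4.4.2.3 assigns scans with both the double-blind and the open-label window tables. The SAP does not say which scans enter the total.

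**The concern.** A per-scan rate is comparable between groups only if a scan stands for about the same amount of time in each. Here it does not. Double-blind intervals are 24 weeks. Open-label intervals are nominally 48 weeks, and the first is longer still for a relapse switcher, because it reaches back to the last double-blind scan. How many long intervals a patient contributes depends on when he or she relapses, which is the outcome expected to differ by arm.

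A second effect arises only if the count uses open-label scans alone. The first open-label scan of a placebo patient who switched at a relapse would then include lesions formed on placebo, and they would be reported as activity on open-label teriflunomide. Lesion-free status would suffer in the same way, since one such lesion removes a patient from the lesion-free group. New/enlarged T2 count is one of the two key secondary imaging endpoints (SAP 2.1.3.2).

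**Working it through.** **1. The plan's own figures.** From 60% placebo relapse at 2 years (Protocol 11.1): -ln(0.4)/2 = 0.4581 per year. Half of that is 0.2291, giving 1 - exp(-2 x 0.2291) = 36.8% on teriflunomide. All three match. Dropout of 20% in 2 years is -ln(0.8)/2 = 0.1116 per year. The Lachin-Foulkes formula with these inputs gives N = 167.5 against the stated 165. The hazards are therefore usable. The plan states no MRI figure.

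**2. Who switches early.** A switch needs a relapse after week 8, so 88 weeks are at risk. Without dropout: 1 - exp(-0.4581 x 88/52) = 54% on placebo and 1 - exp(-0.2291 x 88/52) = 32% on teriflunomide. With the plan's dropout: about 49% and 29%, while about 38% and 55% complete 96 weeks. Early switchers are then 49/(49 + 38), about 57%, of placebo entrants to open label and about 34% of teriflunomide entrants.

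**3. The gap.** Gap = switch week minus last scheduled scan (Week 0, 24, 48 or 72). Simulated at these hazards, the placebo mean is 12.6 weeks (10th to 90th percentile about 3 to 22; maximum 24). The pre-switch share of the first open-label interval is 12.6/(12.6 + 48) = 21%, or 24/72 = 33% at the maximum. A scan at the switch makes the gap 0.

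**4. Count from randomization.** Scans per patient over 192 weeks, counting each scan against the one before:

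| Patient | Scans counted | Number | Weeks per scan |
|---|---|---|---|
| Completer | W24, 48, 72, 96; OL 48, 96 | 6 | 192/6 = 32.0 |
| Switch at week 36 | W24; OL 48, 96, 144, EOT | 5 | 192/5 = 38.4 |
| Switch at week 12 | OL 48, 96, 144, EOT | 4 | 192/4 = 48.0 |

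Averaged over entrants, with dropout, this gives 5.39 scans in placebo/teriflunomide and 5.65 in teriflunomide/teriflunomide. Weeks per scan are 192/5.39 = 35.6 and 192/5.65 = 34.0. At equal lesion rates the per-scan ratio is 5.39/5.65 = 0.95, where it should be 1.00. With an assumed on-drug to placebo lesion-rate ratio of 0.5, the ratio over time is 0.74 and the per-scan ratio is 0.74 x 0.954 = 0.71.

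**5. Count from open-label scans only.** Let theta be the on-drug to placebo lesion-rate ratio. The documents give no lesion rates, so theta is an assumption. For a placebo relapse switcher, the first open-label count is multiplied by 1 + 12.6/(48 x theta).

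| theta | Placebo relapse switcher, first scan | All placebo/teriflunomide, first scan | All placebo/teriflunomide, whole open-label period |
|---|---|---|---|
| 0.3 | 1.87 | 1.49 | 1.19 |
| 0.5 | 1.52 | 1.30 | 1.11 |
| 0.7 | 1.37 | 1.21 | 1.08 |

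The whole-period figure at 0.5: mean open-label duration in the model is about 125 weeks, so 1 + 0.566 x 12.6/(0.5 x 125) = 1.11. A teriflunomide relapse switcher's first scan is multiplied by 1 + 12.6/48 = 1.26, but those lesions formed on drug.

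The group ratio (teriflunomide/teriflunomide over placebo/teriflunomide, per scan) is 1.03 without carry-over, because early switchers tend to have a short last interval. With carry-over it is 0.96 at theta 0.5 and 0.90 at theta 0.3.

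**The case against.** A reader might infer that every first open-label scan credits placebo lesions to open-label teriflunomide. The documents do not support that, for five reasons:

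- Week 96 completers have a scan at the transition.
- High-MRI-activity switchers have just had the Week 36, 48 or 72 scan that triggered the switch.
- The previous-scan remark is written for the switch rule. Applying it to the endpoint is an inference. Counting against baseline would be a different problem.
- SAP 2.4.4 sets randomization as the default start, and the SAP says so explicitly when it wants open-label data only, as for the annualized relapse rate (2.4.4.3.1). Under that default, lesions formed before the switch stay in the placebo/teriflunomide sequence group, where they belong.
- Gd-enhancing lesions are not defined against an earlier scan, so they are not affected.

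There is more on that side. SAP Table 5 has a row for scans up to the first open-label dose, and 2.5.4 places unscheduled scans in windows. Protocol 17.9 records that Amendment 1 intended an MRI at a confirmed relapse. No current visit schedule requires one, but where such a scan was done and was usable the gap would largely close. SAP 2.4.4.2.3 promises a rate per group, without the relative risk and p-value of the double-blind model. SAP 2.4.4 and 2.4.4.4 call these analyses exploratory.

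All of this stands, and it limits the reach and weight of the point. It does not repair the offset: on the from-randomization reading the scan count still stands in for unequal time, and the imbalance still differs by group.

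**Conclusion.** The point holds for patients who switch early after a relapse, and for new/enlarged T2 counts (and new T1 hypointense counts if they are made the same way). The scan-count offset biases the per-scan ratio by about 5% in favour of teriflunomide/teriflunomide if the count runs from randomization. If it uses open-label scans alone, lesions formed on placebo are also counted as open-label activity, moving the group ratio to about 0.96 at an assumed rate ratio of 0.5. Which reading applies cannot be settled from the text.

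These sizes assume counts against the previous scan, scans on schedule, constant lesion rates within treatment, a switch at the time of relapse, all eligible patients entering open label, and no high-MRI-activity switches. Baseline scans may precede randomization by up to 6 weeks, so gaps for switches before Week 24 could be longer than modelled. Severity is low to moderate: the analyses are exploratory and the shift is modest, but the better method costs almost nothing.

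**What to change.** 1. For new/enlarged T2 counts, and new T1 hypointense counts if made the same way, replace the offset with the log of total weeks covered by the counted scans, from the reference scan of the first counted scan to the last counted scan. A total is needed because the response is a per-patient total. Keep the scan-count offset for Gd-enhancing lesions.
2. State the reference scan for a new lesion, and whether the total runs from randomization or uses open-label scans only.
3. If open-label-only counts or lesion-free status are reported, add a sensitivity analysis that omits the first open-label scan when the preceding scan was well before the first open-label dose (for example more than 4 weeks) and uses it only as the new reference. Step 1 does not replace this: at an assumed ratio of 0.5, placebo/teriflunomide would still show (0.5 x 125 + 0.566 x 12.6)/(125 + 0.566 x 12.6) = 0.527 per covered week against 0.5, a ratio of 0.95, because the placebo lesions remain in the count.

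The cost is SAP wording and a re-run of the lesion models, with no new visits or data. The sensitivity analysis loses one scan per early relapse switcher. That loss falls more on placebo/teriflunomide and depends on having relapsed, so it should support the main result and not replace it. The 4-week limit is a convention and can be varied.

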2.4.4.2.4 EDSS

EDSS score and the change from baseline in EDSS score in the double-blind period will be summarized with descriptive statistics at each visit by treatment group.

2.4.4.2.5 Cognitive outcome

The change from baseline in Cognitive Battery Tests and SDMT will be summarized descriptively. Box plot will be provided as well.

2.4.4.2.6 Disease free patient

Disease-free patients were defined as patients with

- No confirmed clinical relapse.
- No 24-week sustained disability progression (≥ 0.5 -point EDSS score increase if baseline EDSS score > 5.5 or ≥ 1 -point EDSS score increase from baseline if baseline EDSS score ≤ 5.5 , persisting for ≥ 24 weeks).
- Free of MRI activity: No Gd-enhancing T1 lesions and no new/enlarging T2 lesions.

Alternative definitions of disease-free status, eg, using cognitive information may be additionally explored.

The proportion of disease-free patient at Weeks 48, 96, 144 and 192 will be summarized based on all patients having an MRI at these time points. Kaplan-Meier methods will be used for estimation.

2.4.4.3 Analysis of additional efficacy endpoint

2.4.4.3.1 Annualized relapse rate

The annualized relapse rate (ARR) is defined as the number of confirmed clinical relapses occurred during the study per patient-year. It will be analyzed in open-label period only. A confirmed clinical relapse is defined as the appearance of a new clinical sign/symptom or clinical worsening of a previous sign/symptom (one that had been stable for at least 30 days) that persists for a minimum of 24 hours in the absence of fever. Each episode of relapse must be confirmed by the treating neurologist, based on the objective assessments by an independent evaluator (the examining neurologist) by documenting either of the following:

- A) A 1-point increase in at least two FS functions, or a 2-point increase in at least one FS function (excluding bowel/bladder and cerebral) from the previous clinically stable assessment, or;
- B) An increase of at least 0.5 point in EDSS score (unless EDSS=0, then an increase of at least 1.0 point is required) from the previous clinically stable assessment.

Relapses are collected on CRF page “MS relapse”. The objective confirmation, based on the protocol-defined criteria, is reported (Yes/No) in the CRF. Only confirmed clinical relapses will be used in the analysis.

A gross estimate of annualized relapse rate for a treatment group would be the total number of relapses for patients in the treatment group divided by the sum of standardized study durations for patients in the treatment group. Total number of confirmed clinical relapses and standardized study duration will be calculated for each patient.

- Total number of confirmed clinical relapses is defined as the number of confirmed clinical relapses with onset between enrollment date of the open-label period and treatment discontinuation/completion date (same as last dose IMP intake date).
- Standardized study duration (in year) will be calculated by (last dose IMP intake date - enrollment date of the open-label period + 1) / 365.25.

Adjusted ARR will be performed using a Poisson regression model with robust error variance that would accommodate the potential over-dispersed data appropriately. The model will include the total number of clinical relapses as the response variable, treatment group as the test variable, pubertal status, and region as covariates. In order to account for different treatment durations among subjects, the log-transformed standardized treatment duration will be included in the model as an “offset” variable for appropriate computation of relapse rate. The robust error variances can be estimated by specifying the patient identifier in the repeated statement using SAS PROC GENMOD, and this is equivalent to the Generalized Estimating Equation (GEE) model. In comparison to the regular Poisson model, the GEE estimator is robust against

violation of the correlation structure and the distributional assumptions. The treatment-by-strata and treatment-by-region interactions will be evaluated separately at the 5% level of significance by adding the corresponding interaction term to the model. If a statistically significant interaction is detected at $p < 0.05$, further investigations will be performed for the possibility of qualitative interaction.

The estimated relapse rates and 2-sided 95% confidence intervals will be provided for each treatment group. Nelson-Aalen mean cumulative function plot will be provided for descriptive purposes.

2.4.4.3.2 *Time to sustained disability progression (using EDSS)*

The time to sustained disability progression will be assessed by EDSS during the study. The first disability progression (ie, confirmed disability worsening) is defined as a sustained increase of at least 1.0 point (0.5 for subjects with baseline EDSS > 5.5) persisting for at least 24 weeks from baseline EDSS in the double-blind period of the study.

The minimum EDSS increase used to define disability progression is referred to as “minimum increase” in the following text. The initial EDSS increase that meets this “minimum increase” criterion is referred to as “the onset”. An EDSS measurement at or after 24 weeks following the onset is necessary to confirm the initial increase and is referred to as “24-week EDSS confirmation”. All EDSS measurements (with or without relapse) will be used to determine the onset of a disability progression. However, for the purpose of confirmation, only EDSS measured more than 30 days after the onset of a confirmed relapse will be used to avoid a confirmation caused by a temporary relapse. In order to confirm that the EDSS increase is persistent for at least 24 weeks, the following conditions have to be satisfied: (1) The 24-week EDSS confirmation needs to maintain at least the minimum increase; (2) all EDSS measurements between the onset and the 24-week EDSS confirmation need to maintain at least the minimum increase. Once a disability progression is confirmed, time to disability progression is defined as “date of onset - date of randomization (in the double-blind period) + 1”. If a patient has no disability progression on or before last during treatment EDSS evaluation, then the patient is considered as disability progression free until the date of last during treatment EDSS evaluation. The last during treatment EDSS evaluation is defined as last measurement during treatment period (measurement at last scheduled visit for patients who complete the treatment, or measurement at the close-out visit for patients who discontinue the treatment).

If a patient dies for any reason without a 24-week EDSS confirmation, the disability progression will be considered as confirmed with the date of the onset as the date of progression unless any EDSS measured within the 24 weeks did not maintain the minimum increase. Death due to MS (EDSS=10) will be counted as confirmed progression. The progression date is the date of death if there is no prior qualifying EDSS increase and it is the date of the first qualifying EDSS increase if there is such an EDSS increase prior to the death. All the derivation will be based on the exact EDSS evaluation date. Since the actual visit may have been ± 7 days from the scheduled visit, a -7 days window will be used to define the period of 24 weeks.

Censoring rules

- If a patient has no EDSS increase that meets the criteria for progression before treatment discontinuation/completion, then the patient will be considered as free of progression till the date of last during-treatment EDSS evaluation.
- If a patient has an EDSS increase that meets the criteria for progression before treatment discontinuation, all available EDSS assessments obtained during the follow-up visits will be used to serve the purpose of progression confirmation. The patient will be considered as having disability progression if the first increase during treatment period is confirmed for at least 24 weeks during the follow-up visits. If the EDSS from the follow-up visit(s) does not confirm a sustained increase or despite all possible attempts, no confirmatory EDSS assessment is obtained after withdrawal, the patient will be considered as free of disability progression until the date of last during treatment EDSS evaluation.
- If a patient has an EDSS increase that meets the criteria for progression and completes the treatment period before the progression can be confirmed, then the patient will be considered as free of progression till the date of last during-treatment EDSS evaluation.
- In rare cases, if a patient had a delayed EDSS scheduled during the open-label period but performed during the optional extension period due to the Covid-19 pandemic, then this assessment will still be considered as during-treatment EDSS evaluation. The delayed EDSS result will be considered in the sustained disability progression determination process in the open-label analysis.
- In rare cases, if a patient had a delayed EDSS scheduled during the open-label period but performed after treatment discontinuation due to the Covid-19 pandemic, then the delayed EDSS result will be used for progression confirmation purpose only.

The hazard ratio and 95%CI for teriflunomide/teriflunomide versus placebo/teriflunomide will be estimated using Cox regression model with treatment group, region and baseline pubertal status as covariates, offset by the lengths of individual observations.

The Kaplan-Meier method will be used to estimate median time (if possible) to disability progression sustained for at least 24 weeks and cumulative disability progression rates specific to each treatment group. Kaplan-Meier graphs will be generated; quartiles and point probabilities will be calculated. Interval estimates will be calculated using 95% point wise confidence intervals.

